5.1.1 Laboratory Evaluations

A fasting blood sample will be performed for the laboratory evaluations described in section 5.1.1.1.

5.1.1.1 Table: Clinical Laboratory Tests

Tests	
Lipid panel (TG, TC, HDL-C, LDL-C)	Measured at CHOP Clinical Lab
Non-HDL cholesterol	Calculated as Total cholesterol – HDL-C from the lipid

	panel
Lipoprotein subclass analysis	By LipoScience, Inc. (Raleigh, NC) using NMR spectroscopy
Blood glucose	Measured in duplicate at study site on NOVA Biomedical STAT strip meter
Plasma immunoreactive insulin	Measured in duplicate by ELISA in the CHOP CTRC Biochemistry Core Lab
Insulin resistance	Fasting insulin and glucose used to calculate Homeostasis Model Assessment-Insulin Resistance Index (HOMA-IR): [fasting insulin (uIU/mL) x fasting BG(mmol/L)]/22.5
Thyroglobulin antibody	Measured at CHOP Clinical Lab
Thyroid peroxidase antibody	Measured at CHOP Clinical Lab
High sensitivity C-reactive protein (hs-CRP)	Measured in the Penn CTRC TCL
Interleukin 6 (IL-6)	Measured at CHOP CTRC Biochemistry Core Lab using R&D kits
PAI 1	Measured at CHOP CTRC Biochemistry Core Lab using R&D kits
HbA1c	Measured at CHOP Clinical Lab
Adiponectin & Leptin	Both measured in duplicate at CHOP CTRC Biochemistry Core Lab using Alpco kits
TSH & T4	Measured at CHOP Clinical Lab

5.1.1.2 Pregnancy Testing

A urine pregnancy test will be performed for female subjects who are ≥ 11 years old or who are menarchal during the following visits: screening/baseline, 6 month, 12 month, and 18 month. A positive pregnancy result will be disclosed to the participant only. Pregnancy results will be disclosed to the parent/guardian if the subject gives the investigators permission. Subjects found to be pregnant during the visit will not be able to enroll in this study. The investigators will counsel the subject and guide them to seek the appropriate care.

5.2 Safety Evaluation

Subject safety will be monitored by adverse event reporting, vital signs, physical examinations, and TSH levels. This protocol involves a very small radiation exposure, which is unlikely to cause any untoward effects to the participant. However, because the protocol may be unsafe to an unborn child, pregnancy is an exclusion criterion of the study.

6 STATISTICAL CONSIDERATIONS

6.1 Statistical Methods

6.1.1 Baseline Data

Data management will proceed as with Aim 1, with particular attention to obtaining all information on each subject at each encounter. Subject retention in our previous studies of children with DS has been excellent.

Estimates will be based on a standard mixed effects piecewise longitudinal data model⁽²⁾, implemented in the Stata v 12 program “xtmixed”, to estimate in a single model both longitudinal (within subject) and cross-sectional (across subject) effects of the intervention. Cross-sectional comparisons will be possible for the second 6-month period of observation when ½ of subjects will be switched to treatment while the other ½ will take a placebo. A piecewise model allows for a change in trajectory of an endpoint upon start of the intervention and for a possible shift in pattern of endpoint values soon after intervention, thus allowing for contrasts of both levels and trajectories. After descriptive statistics, mixed effects linear regression, with random intercepts for subject-specific baseline z-score, and random slopes (for inter-subject variation in trajectories over time), will model and compare outcomes over time. Inclusion of quadratic terms for time, and implementation of splines, will avoid unrealistic assumptions of linear changes in outcomes^(25, 26). Baseline covariates and auxiliary variables that predict dropout will be included to adjust for any residual imbalance and to meet the model assumption of dropout at random. Multiple imputations will be used for any missing covariates⁽²⁷⁾.

Primary comparisons will assume complete treatment adherence. Using the methods of Nagelkerke⁽²⁸⁾ and Small⁽²⁹⁾, we will estimate the effect of the intervention among those subjects who adhered to treatment. Robust confirmatory analysis will use generalized estimating equations weighted to adjust for dropout⁽³⁰⁾.

Key contrasts will compare the level of each endpoint before and after treatment by comparing differences of model-based expected values at the end of treatment and expected values at baseline; expected values arise from implementation of mixed effects models. This approach permits adjustment for relevant changes in patient characteristics over time (e.g. changes in growth and pubertal status) and for any baseline factors predicting dropout. Alternative contrasts will compare slopes of endpoints over time prior to the intervention against the slopes after treatment initiation. Pre-intervention measures will improve statistical power.

Sensitivity analyses will examine the potential impact of informative dropout⁽³¹⁾, although this source of bias will be minimized through subject retention and follow-up after dropout⁽³²⁾. Supplementing models will be complete descriptive reports, including graphical displays of cholesterol and BMI-Z trajectories for each subject.

Potential Problems/Feasibility: Dosing of levothyroxine treatment tends to be weight-based and is not an exact science. The starting daily dose of 0.5-1 mcg/kg/day is less than

full replacement doses since TSH will be in the 5-10 mUI/mL range and we wish to avoid “over-supplementing” and suppressing TSH. TSH will be rechecked 6 weeks after levothyroxine initiation to confirm TSH is in the desired range. After 6 weeks some subjects may not have “optimal” TSH levels and dose adjustments will be required. We expect that by 3 months following levothyroxine initiation, all subjects will have TSH in the desired range, allowing an additional 3 months for the effect of intervention to be realized; in fact, the immediate treatment group will be followed for 12 months, over which time effects upon body composition and CMR factors should be apparent. This study might find that the relationship between subclinical hypothyroidism and CMR factors is pure association, an important finding as the medical community looks for evidence upon which to base management of “mild” TSH elevations in DS. In fact, this finding could avert unnecessary treatment of subclinical hypothyroidism in adolescents with DS.

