
3.1.1 Screening Phase

Potential subjects will be identified using the protocol inclusion and exclusion criteria. With their permission, subjects may be screened and recruited from Aim 1: Cardio risk factors in DS youth (IRB #12-009233), which is recruiting male and female subjects with Down syndrome in the age range of 10-20 years of age. Additional children will be recruited from local primary care pediatric practices and from the Division of Endocrinology where children with DS are routinely referred for thyroid function abnormalities. A telephone interview and medical record review to determine eligibility will be conducted on subjects who are not recruited from #9233.

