3.2 Allocation to Treatment Groups and Blinding

Randomization and allocation concealment: Children will be randomized to two groups. Both will be observed for 6 months. One will be switched to the intervention at 6 months, and continued thereafter. The other will be switched to placebo at 6 months and to the intervention at 12 months. Randomization will be performed centrally by the project statisticians and implemented using opaque sealed envelopes to ensure allocation concealment. Balance between treatment arms will be maintained by use of randomly permuted blocks with unequal block sizes and with stratification by patient gender (two

strata, male and female and age (two strata, ages 8-14 and ages 14-20). After envelopes are opened, treatment assignment will be blinded to the subjects (and their parents).

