4.3 Treatment Phase

4.3.1 Randomization

After Study Visit #2 (6 months), only subjects with persistently elevated TSH (5-10 mIU/mL) will be randomized into two groups of 10. Randomization will be performed centrally by the project statisticians and implemented using opaque sealed envelopes to ensure allocation concealment. Balance between treatment arms will be maintained by use of randomly permuted blocks with unequal block sizes and with stratification by patient gender (two strata, male and female) and age (two strata, ages 8-14 and ages 14-20). After envelopes are opened, treatment assignment will be blinded to the subjects and their parents/guardians.

The following visits and procedures will occur during the Treatment Phase:

Blood Draw Visit B (7.5 month): Approximately 15 minutes for blood draw

TSH and T4 blood draw will be done 6 weeks after the 6 month visit (at 7.5 months) as a measure of efficacy of levothyroxine dose.

Study Visit #3 (12 month) = 1 visit lasting approximately 4 hours

- Fasting blood draw: 15 minutes
- Pubertal Status Exam: 5 minutes
- Vital Signs: 10 minutes
- DXA scan: 10 minutes
- Anthropometric measurements: 15 minutes
- Family history: 10 minutes
- Questionnaire assessments (PedsQL, IWQOL, BES, FRS, ASAQ, CEBQ, CFQ, ABAS-II, HFI): 1.5 hours, or as long as needed by subject and parent/guardian. HFI will be mailed to family and completed prior to visit.
- Physical activity armband (worn at home for 7 days)
- 3 day dietary recalls over the phone from home = Approximately 30 minutes for each diet recall.

Blood Draw Visit C (13.5 month): Approximately 15 minutes for blood draw

TSH and T4 blood draw will be done 6 weeks after the 12 month visit (at 13.5 months) as a measure of efficacy of levothyroxine dose.

Study Visit #4 (18 month) = 1 visit lasting approximately 4 hours

- Fasting blood draw: 15 minutes
- Pubertal Status Exam: 5 minutes
- Vital Signs: 10 minutes
- DXA scan: 10 minutes
- Anthropometric measurements: 15 minutes
- Family history: 10 minutes
- Questionnaire assessments ((PedsQL, IWQOL, BES, FRS, ASAQ, CEBQ, CFQ, ABAS-II, HFI): 1.5 hours, or as long as needed by subject and parent/guardian. HFI will be mailed to family and completed prior to visit.
- Physical activity armband (worn at home for 7 days)
- 3 day dietary recalls over the phone from home = Approximately 30 minutes for each diet recall.

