6.1.2 Efficacy Analysis

Key contrasts will compare the level of each endpoint before and after treatment by comparing the differences of model-based expected values at the end of treatment and expected values at baseline. These expected values will arise out of the implementation of mixed effects models that will adjust for any relevant changes in patient characteristics over time (such as changes in growth and pubertal status) as well as for any baseline factors that predict dropout. Alternative contrasts will compare the trajectories (slopes) of endpoints over time prior to the intervention against the slopes after the start of treatment.

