6.2 Sample Size and Power

Target sample size is 20, but 29 subjects will be enrolled to allow for dropout. Assuming that the dependent variables are continuous, the power calculations using nonparametric tests that would be suitable for both continuous and ordered data are listed below:

Correlation over time	Effect size of interaction (SD)	Power
0.5	0.7	0.84
0.6	0.6	0.71
0.8	0.4	0.82

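### Randomisation is stratified by sex and age, but section 6 names neither factor as a model term, so the between-arm contrast for months 6 to 12 may lose precision

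*Combined protocol and SAP*

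**What the plan says.** Section 4.3.1 uses randomly permuted blocks "with stratification by patient gender (two strata, male and female) and age (two strata, ages 8-14 and ages 14-20" years. Section 3.2 gives the same factors and the same bands. Together they make four cells for two groups of 10.

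Section 6.1.1 describes one mixed model for both within-subject and between-subject effects. On the latter it says "Cross-sectional comparisons will be possible for the second 6-month period of observation", when one half is on levothyroxine and the other half on placebo.

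Covariates are described in three places:

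- Early in 6.1.1: "Baseline covariates and auxiliary variables that predict dropout will be included to adjust for any residual imbalance", with a second stated purpose of supporting the dropout-at-random assumption.
- Later in 6.1.1, for the key contrasts: "adjustment for relevant changes in patient characteristics over time (e.g. changes in growth and pubertal status) and for any baseline factors predicting dropout".
- In 6.1.2, after changes in growth and pubertal status: "as well as for any baseline factors that predict dropout".

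Nowhere in section 6 is sex, age or stratum given as a model term.

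**The concern.** Stratified blocks balance the arms on sex and age. If those factors predict the outcome, balancing them reduces the true sampling variance of the between-arm difference. A model without the factors leaves their contribution in the residual and does not credit that reduction. Its standard error is too large and, with a t reference, the test is conservative.

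Months 6 to 12 give the only concurrent comparison with placebo, with about 10 subjects per arm, so there is little precision to spare. The primary endpoint in section 2.1, non-HDL-C, is total cholesterol minus HDL-C (table in section 5.1.1.1), and no standardisation for age or sex is described. Leaving the covariates unnamed also leaves a modelling choice open until the data are seen, in a trial whose investigators know the treatment arm.

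**Working it through.** **1. Inputs.** From the documents: 20 completers (6.2), two groups of 10, sex by two age bands, permuted blocks of unequal size (4.3.1), and an effect of 0.7 SD at correlation 0.5 (6.2). Assumed, because the documents do not say: block sizes 2 and 4, two-sided 0.05, complete data, and the share R² of the variance of 6-month change explained by the factors (0 to 0.3, half from each).

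**2. The plan's own figures.** Section 6.2 states power of 0.84, 0.71 and 0.82. No single method tried returns all three. A two-sided paired t test on 20 gives 0.84, 0.81 and 0.77; a two-arm z test on change with 10 per arm gives 0.35, 0.32 and 0.29. This point does not rest on that table. It takes only the effect size from it, converted as d/√(2(1−ρ)), if SD means the SD at one visit:

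- 0.7/√(2×0.5) = 0.70 SD of change
- 0.6/√(2×0.4) = 0.67
- 0.4/√(2×0.2) = 0.63

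**3. Size of the mechanism.** With the SD of change set to 1, the model standard error without the factors is about √(1/10 + 1/10) = 0.447. With perfect balance within strata the true value is about √((1−R²)×0.2). That is 0.424, 0.400 and 0.374 at R² = 0.1, 0.2 and 0.3.

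**4. Change-score simulation.** n = 20, t reference, comparing arm only with arm plus sex and age stratum.

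| R² | Model SE, no factors | True SE, no factors | Type I, no factors | Power at 0.7 SD, without | Power at 0.7 SD, with |
|---|---|---|---|---|---|
| 0 | 0.443 | 0.452 | 0.052 | 0.32 | 0.31 |
| 0.1 | 0.444 | 0.428 | 0.043 | 0.31 | 0.34 |
| 0.2 | 0.445 | 0.410 | 0.034 | 0.31 | 0.38 |
| 0.3 | 0.446 | 0.385 | 0.026 | 0.29 | 0.42 |

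The standard errors come from a separate run of 20,000 data sets per R². Its power was 0.323, 0.307, 0.297 and 0.282 without the factors, and 0.316, 0.330, 0.370 and 0.408 with them. It agrees with the table to within about 0.013. Type I error with the factors was 0.053, 0.049, 0.051 and 0.050.

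**5. Reference distribution.** With a normal instead of a t reference (12,000 runs), type I error at R² = 0, 0.1, 0.2 and 0.3 is 0.065, 0.057, 0.043 and 0.034 without the factors, and 0.068, 0.071, 0.066 and 0.064 with them. Adjustment should therefore be paired with a small-sample reference.

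**6. Closer to the plan.** Four visits, random intercept and slope, categorical visit, 10% of residual change variance from random slopes (assumed), t with 18 df, 8,000 runs per scenario. Power at 0.7 SD when the stratum effect is linear in time:

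| R² | No factors | Main effects | Plus interaction with the month 6 to 12 term |
|---|---|---|---|
| 0 | 0.393 | 0.393 | 0.386 |
| 0.1 | 0.373 | 0.385 | 0.407 |
| 0.2 | 0.348 | 0.366 | 0.407 |
| 0.3 | 0.356 | 0.389 | 0.435 |

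Main effects gain 1 to 3 points at R² of 0.1 to 0.3; adding the interaction brings the gain to 3 to 8 points. The change score gained 3 to 13 (0.34−0.31 up to 0.42−0.29). The reason is that a main effect shifts all visits alike, which the random intercept largely absorbs, whereas a factor acting on change needs the interaction. If the stratum effect arises only in months 6 to 12, power with the interaction goes from 0.407 to 0.425, 0.427 to 0.476 and 0.428 to 0.510 at R² = 0.1, 0.2 and 0.3.

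**7. Before-after contrast.** With complete data and expected values averaged over the sample, adding centred factors to a regression of paired change moved the mean change by at most 4×10⁻¹⁶ in 2,000 data sets. The estimate is the same.

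**The case against.** The early sentence in 6.1.1 can be read so that only the auxiliary variables need predict dropout. Baseline covariates entered for residual imbalance would then be the natural place for sex and age. That reading is fair, and it rules out saying that the plan excludes the factors. It does not name them, though, and the two later statements use the narrower wording.

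The size is also open to challenge. No document gives an R² for change. The simulated comparator has no covariates at all, whereas the plan adjusts for growth and pubertal status, which may carry part of an age or sex effect. The plan's quadratic and spline time terms were not simulated, nor was dropout, although 29 are enrolled to obtain 20. For BMI-Z, standardisation should absorb some of the effect. These objections stand: the power figures illustrate the mechanism and are not properties of this plan.

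Factor-by-period interactions in 20 subjects over four cells are debatable, so they are not made a requirement here.

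A reader might infer that the omission biases the treatment effect or raises false positives. The checks do not support that. Omitting the factors lowered type I error wherever they were prognostic. The excess seen with a normal reference belongs to that reference and is larger with the factors included.

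**Conclusion.** The point holds as a minor one. Section 6 can be followed exactly with the randomisation factors left out. If they predict 6-month change, the months 6 to 12 between-arm contrast then has an overstated standard error and lower power. The illustrative loss is about 3 to 13 points at R² of 0.1 to 0.3 in the change score, and probably less in the planned mixed model. It rests on the assumed R², assumed block sizes, complete data and a t reference. At R² = 0 nothing is lost by omission.

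The key before-after contrast is essentially unaffected.

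Both randomisation sections put age 14 in two bands: "age (two strata, ages 8-14 and ages 14-20". A reader might infer that this undermines the randomisation. The documents do not support that. It is a wording point, touching about 20/13 = 1.5 of 20 subjects if ages are completed years spread evenly over 8 to 20 (an assumption), and almost none if exact ages are used. It matters here only because the stratum must be defined before it can be a model term.

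**What to change.** In section 6.1.1, state that sex and randomised age stratum enter the primary model as fixed effects whether or not they predict dropout. State also that the between-arm contrast is tested with a small-sample t reference, and name the degrees-of-freedom method.

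As an option or sensitivity analysis, add the interaction of both factors with the month 6 to 12 term, since main effects alone may gain little if the factors act on change.

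In sections 3.2 and 4.3.1, give age bands that do not overlap, for example 8 to under 14 and 14 to 20, by age on the date of randomisation.

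The cost is a sentence or two in 6.1.1, a clause in each randomisation section and two model terms (four with the interaction). If the factors are not prognostic, the price is about 1 point of power: 0.323 to 0.316 in the change score, and 0.393 to 0.386 in the four-visit model with the interaction. With dropout, which was not simulated, the cost could be larger.

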Study Treatment: A single blinded randomized trial of levothyroxine treatment (starting dose 0.5 – 1 mcg/kg daily) using a switching replication design. Subjects will be randomized into 2 groups of 10.

(Group 1) Delayed treatment group: 6 months of placebo followed by 6 months of levothyroxine treatment

(Group 2) Immediate treatment group: 12 months of levothyroxine treatment

Follow-Up: Studies will be obtained at baseline, 6 months, 12 months, and 18 months. Interim thyroid studies will be checked at 3 months, 6 weeks after randomization (month 7.5); month 13.5 and 6 weeks after any dose adjustment.

Efficacy Evaluations

TSH

T4

Anthropometry (HT-Z, WT-Z, BMI-Z),

body composition by DXA,

PWV & PWA

Blood lipid panel, non-HDL-C, lipoprotein subclass analysis, glucose, plasma insulin, HOMA-IR, hs-CRP, IL-6, PAI-1, adiponectin, leptin,

QOL, Body Image, physical activity assessment.

Safety Evaluations

To monitor for safety, data will be made available to investigators every 3 months. The PI will not be blinded to the treatment arm, will be making dose adjustments, and for safety purposes, TSH and T4 data will be available to the PI as soon as it is available.

Interview at 4 and 6 weeks after treatment initiation and at each visit to document intensity and frequency of any AE.

Any AEs and SAEs will be reported to the CTRC and the IRB within the allotted time frame.

Statistical And Analytic Plan

Standard mixed effects piecewise longitudinal data model ⁽²⁾ will be used to estimate in a single model both longitudinal (within subject) and cross-sectional (across subject) effects of the intervention. Cross-sectional comparisons will be possible for the second 6-month period of observation when ½ of subjects will be switched to treatment while the other ½ will take a placebo.

DATA AND SAFETY MONITORING PLAN

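### No small-sample method is specified for a GEE and a mixed model on about 20 subjects; if the GEE is left uncorrected, its real type I error is about 7-9% and its intervals are too narrow

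*Combined protocol and SAP*

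**What the plan says.** Section 6.1.1 of the combined protocol and SAP makes a mixed-effects piecewise model the main analysis, "implemented in the Stata v 12 program" xtmixed, with random intercepts and "random slopes (for inter-subject variation in trajectories over time), will model and compare outcomes over time". Quadratic time terms, splines and covariates are also foreseen. As a check on this model it adds: "Robust confirmatory analysis will use generalized estimating equations weighted to adjust for dropout".

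The size is set in section 6.2: "Target sample size is 20, but 29 subjects will be enrolled to allow for dropout". The Protocol Synopsis gives the allocation, "Subjects will be randomized into 2 groups of 10", and the main measurement times: "Studies will be obtained at baseline, 6 months, 12 months, and 18 months".

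Sections 6.1 to 6.3 do not state:
- an alpha level or sidedness;
- ML or REML for the mixed model;
- a degrees-of-freedom method, or a z or t reference, for either analysis;
- a working correlation, variance estimator or small-sample correction for the GEE.

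**The concern.** The sandwich variance of a GEE is justified when there are many independent clusters. Here the clusters are children, and there are about 20. At that size the plain sandwich variance is biased downward, and a normal reference ignores the uncertainty in the variance estimate. Both errors make the standard error or the critical value too small.

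The protocol calls this analysis both robust and confirmatory. If it were run with standard large-sample inference, it would hold its nominal error rate less well than the mixed model it is meant to check. In a preliminary study of 20 children the interval is the main product, so its width should be right. Section 6.1.1 also says that a finding of no effect could spare unnecessary treatment, so an interval that is too short can mislead in either direction.

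**Working it through.** **Plan's own figure.** The plan states no alpha or type I error, so there is no figure of that kind to reproduce. The only operating characteristics are the powers in section 6.2 (0.84, 0.71, 0.82). A paired two-sided 5% t test with n = 20 and SD of change sqrt(2(1 - rho)) gives 0.844, 0.812 and 0.765, so only the first row agrees. That mismatch is a separate matter and does not enter the calculation below.

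**Inputs.** 20 subjects, 10 per arm, visits at 0, 6, 12 and 18 months, and correlations of 0.5, 0.6 and 0.8 (Synopsis and section 6.2). Assumed: two-sided alpha of 5%, normal errors, and, for the uncorrected case, a plain sandwich variance with a z reference.

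**Closed form, between-arm contrast of change.** With n per arm, the plain sandwich variance is (n - 1)/n times the unbiased variance. The z test therefore rejects when |t| with 2n - 2 df exceeds 1.96 x sqrt((n - 1)/n). The correct critical value is the 97.5% point of that t distribution.

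| n per arm | df | effective cut-off | real size | correct t cut-off | interval too short by |
|---|---|---|---|---|---|
| 10 | 18 | 1.96 x sqrt(0.9) = 1.859 | 7.9% | 2.101 | 1 - 1.859/2.101 = 11.5% |
| 9 | 16 | 1.848 | 8.3% | 2.120 | 12.8% |
| 8 | 14 | 1.833 | 8.8% | 2.145 | 14.5% |
| 7 | 12 | 1.815 | 9.5% | 2.179 | 16.7% |

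**Closed form, within-subject contrast.** The key contrasts in 6.1.2 compare levels before and after treatment. Treated as a one-sample mean change in 20 children, the cut-off is 1.96 x sqrt(19/20) = 1.910 on 19 df. The size is 7.1%. The correct cut-off is 2.093, so the interval is 1 - 1.910/2.093 = 8.7% too short.

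**Simulation of the GEE under no effect** (4 visits, several mean models, with and without random slopes and covariates, 4,000 runs per scenario). Loss after randomisation is not stated, so it was varied. The 31% is (29 - 20)/29 and includes losses before randomisation.

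| GEE inference | real size |
|---|---|
| Plain sandwich, z, N = 20, no dropout | 7.1-8.6% |
| Plain sandwich, z, N = 20, 20% weighted dropout | 7.7-9.1% |
| Plain sandwich, z, N = 29, 31% weighted dropout | 7.4-7.9% |
| N/(N - 1) factor only, z, N = 20 | 6.6-8.5% |
| Mancl-DeRouen, z, N = 20 | 5.0-6.1% |
| Kauermann-Carroll, t, N = 20 | 4.3-5.8% |
| Mancl-DeRouen, t, N = 20 | 3.4-4.7% |

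**Mixed model with a z reference, N = 20.** In the balanced two-arm case with unbiased (REML-type) variance, P(|t18| > 1.96) = 6.6%. With ML variance the factor 0.9 returns and the size is 7.9%. Simulation with random intercept and slope (1,500 runs each, Monte Carlo standard error about 0.6 points) gave 5.3-6.6% for REML and 6.0-7.3% for ML. Some fits lay on the boundary or gave convergence warnings; they were counted whenever a finite standard error was returned. With unbiased variance and t on 18 df, the balanced case returns to 5.0%.

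**The case against.** The strongest reply is that the plan does not say its inference will be uncorrected. It is silent, and a competent analyst could apply a correction without being told. This stands: the 7-9% is conditional on a plain sandwich and a z reference, and both are assumptions. The silence still leaves the choice open, and the usual large-sample form would be too liberal here.

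A reader might infer that the main analysis also has a real error of 8-9%. It does not: a z-based mixed model comes to about 5-7% under REML and 6-8% under ML. Even for the GEE, 8-9% is only the upper part of the range. At 20 completers the closed forms give 7.1% and 7.9%; values of 8.8% and 9.5% need 8 and 7 per arm, below target.

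A reader might also infer that the trial would declare success too easily. The documents do not support that. No success or confirmation criterion is tied to the GEE, section 9.4.1 excludes formal stopping for superiority or futility, and section 1.1 describes the study as preliminary. The GEE stands beside the mixed model, dropout sensitivity analyses and plots of individual trajectories.

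Finally, the 5% benchmark is not in the documents. At another alpha the percentages would differ, but the downward bias in the variance would remain.

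**Conclusion.** The point holds as a gap in specification with a conditional size. With about 20 subjects and a two-sided 5% alpha (assumed), an uncorrected sandwich GEE with a z reference has a real type I error of about 7-9%. Its 95% intervals are about 9-11% too short at the target size, and up to 17% too short at 7 per arm. Enrolling 29 does not cure this: with 31% dropout the simulated error was still 7.4-7.9%. The mixed model is only mildly affected.

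The consequence is overstated precision in a supporting analysis, not a wrong decision rule. The simulated figures rest on normal errors and the correlations in section 6.2. This is a cheap improvement rather than a flaw that invalidates the plan.

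**What to change.** Amend section 6.1.1 as follows:
- State alpha and sidedness.
- Fit the mixed model by REML with a small-sample degrees-of-freedom method (Kenward-Roger or Satterthwaite), and name software that provides it. Section 9.2 already lists SAS beside Stata.
- For the weighted GEE, specify the working correlation, a bias-corrected sandwich variance (Kauermann-Carroll or Mancl-DeRouen) and a t reference with stated degrees of freedom.

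In the simulations, bias correction with a t reference brought the GEE error to 3.4-5.8%. The change needs no new subjects, visits or data. The price is GEE intervals about 10-20% wider: 2.093/1.910 = 1.10 for the within-subject contrast, 2.101/1.859 = 1.13 at 10 per arm and 2.179/1.815 = 1.20 at 7 per arm. Mancl-DeRouen with a t reference is slightly conservative (3.4-4.7%).
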